## **ABBREVIATIONS**

AKI acute kidney injury

SCr serum creatinine

AKD Acute kidney disease

## INTRODUCTION

Surgery alone, or in combination with neoadjuvant chemoradiation therapy, is still considered to be the cornerstone treatment for locally advanced esophageal cancer . Esophagectomy serves as an exemplar of major operative trauma, with well-known risk of pulmonary, cardiac, anastomotic, and septic complications and the presence of postoperative complications after esophagectomies for cancer is associated with a reduced long-term survival . There is a paucity in the literature regarding postoperative renal outcomes after esophageal surgery, with a wide range of incidence.

McCulloch et al  reported in 2003 the results of the British ASCOT prospective database collecting data from 955 patients (ASA score of 3-4 in 25%), of whom 229 underwent esophageal surgery. They found an incidence of renal complications of 3.5%, but no definition of renal complication was present in the study.

Lee et al  in 2014 investigated retrospectively 595 patients underwent esophageal surgery for cancer in South Korea. AKI according AKIN criteria was found in 35.3% of the population with a mean age of 62 years and mainly ASA score 2 (91.8%). AKI was also associated with longer hospital stay.

Moore et al  compared in a retrospective analysis of 150 patients underwent complex or non-complex esophageal reconstruction in 2016, reporting an incidence of renal insufficiency in 1.3% of the entire population, without reference of any diagnostic criteria.

In 2017 Konda et al  performed a retrospective study on 897 patients with a mean age of 61 years and mainly ASA 3 (83.6%) in USA, of whom 11.9% fulfilled the AKIN criteria for AKI.

Wang et al  showed in a Chinese retrospective case-control study published in 2017 a very low incidence of AKI according RIFLE criteria (2.4%) in a population of 2094 patients with a median age of 62 years and with ASA score of 2 in 84% of the patients.

The most recent study by Murphy et al  published in 2020 on 1135 patients with a mean age of 64 years underwent esophageal cancer surgery in three high-volume centers in Ireland showed an incidence of AKI (defined by AKIN criteria) of 18.3%, associated with atrial fibrillation and longer hospital stay.

## **AIM OF THE STUDY**

The aim of this study is to evaluate the incidence of postoperative AKI in patients undergoing elective esophageal cancer surgery. Secondary, we will assess the progression of the acute injury and the association with adverse pulmonary, cardiac, anastomotic, and septic events, as well as mortality. We will also identify risk factors associated with AKI occurrence.

## **STUDY DESIGN**

Retrospective study

## **METHODS**

### **STUDY SETTING, POPULATION**

All patients underwent elective esophagectomy at the Ospedale-Università di Padova

### **PATIENT SELECTION CRITERIA**

#### **INCLUSION CRITERIA**

- Elective esophagectomy

#### **EXCLUSION CRITERIA**

- Age < 18 years;
- End-stage renal disease
- Missing data for AKI definition (serum creatinine or urine output)
- Second surgery (for patients having multiple surgeries performed during a 30-day period, only the first in each period was included)

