### **Assessment of renal function**

“Acute kidney injury” (AKI) is defined as an increase in serum creatinine (SCr) by  $\geq 0.3$  mg/dL within 48 h the baseline value (as determined by all available SCr values from hospital and outpatient medical records within the previous 90 days) or urine output  $< 0.5$  mL/kg/h for 6 h. For those who do not have available baseline SCr levels, expand the screening criteria to an increase or decrease in SCr by 0.3 mg/dl during hospital stay. Second, these suspected AKI were reviewed on a case-by-case basis to confirm the diagnosis. Positive fluid balance and hemodilution are considered in the diagnosis and staging of AKI using the following formula:

Adjusted SCr level = SCr  $\times$  correction factor

where the correction factor = (weight (kg) upon hospital admission  $\times$  0.6 +  $\Sigma$  (daily cumulative fluid balance (L)))/hospital admission weight  $\times$  0.6

The estimated glomerular filtration rate is determined using SCr. Chronic Kidney Disease-Epidemiology Collaboration equations.

Persistent acute kidney injury (AKI) is defined by the continuance of AKI by serum creatinine or urine output criteria (according KDIGO criteria) beyond 48 h from AKI onset. Complete reversal of AKI by KDIGO criteria within 48 h of AKI onset is defined transient AKI.

Acute kidney disease (AKD) is defined as a condition wherein criteria for AKI stage 1 or greater persists  $\geq 7$  days after surgery.

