### Exclusion criteria:

- Age < 18 years.
- ongoing KRT or ESRD.
- Missing data for AKI criteria (serum creatinine and urine output).
- Second surgery.

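### The protocol's exclusion list, the case report form and the renal-function section do not agree on patients without a baseline creatinine, and the fallback screen for them does not match the 48-hour primary endpoint

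*Combined protocol and SAP*

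**What the plan says.** Four places bear on this.

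- **Exclusion Criteria (protocol body):** patients are excluded for "Missing data for AKI definition (serum creatinine or urine output"). Baseline is not mentioned.
- **Exclusion criteria (case report form):** the parallel line is "Missing data for AKI criteria (serum creatinine and urine output"), with *and* where the body has *or*.
- **Assessment of renal function:** AKI is a creatinine rise of at least 0.3 mg/dL within 48 h, measured against a baseline "as determined by all available SCr values from hospital and outpatient medical records within the previous 90 days". The alternative limb is "or urine output" below 0.5 mL/kg/h for 6 h. A separate rule follows: "For those who do not have available baseline SCr levels, expand the screening criteria to an increase or decrease in SCr by 0.3 mg/dl". Its window is given as "during hospital stay". Then "these suspected AKI were reviewed on a case-by-case basis to confirm the diagnosis". The section does not say what standard the review applies, who carries it out, or whether it is blinded.
- **Primary Endpoints:** the endpoint is the incidence of KDIGO AKI in the first 48 hours after surgery.

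No section says whether a missing baseline is missing data for the purpose of exclusion, or whether a fallback case must fall inside the 48 hours to count.

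**The concern.** The creatinine limb of the main definition needs a baseline. A data abstractor with a patient who has none can reasonably exclude that patient under the eligibility list, or keep the same patient under the fallback rule. The denominator then depends on who reads the protocol.

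If the patient is kept, cases are found differently from everyone else's. The fallback differs from the main rule in direction (rise or fall, against rise only) and in window (whole stay, against 48 h). A fall from an early postoperative value shows that creatinine was higher before. By itself it does not show that injury began after surgery, and it gives no onset time, although the same section counts transient and persistent AKI from onset. A change late in the stay is outside the primary window.

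At stake are the single primary endpoint, the outcome of the risk-factor model, and the event rate from the 100-patient pilot on which the Sample Size section relies.

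**Working it through.** **Step 1. The exclusion wordings and the fallback, side by side.** Both exclusion lines are read literally, so *or* excludes if either item is missing and *and* excludes only if both are.

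| Patient's data | Protocol body | Case report form | Renal-function section |
|---|---|---|---|
| No creatinine, urine output recorded | excluded | kept | urine limb can be applied |
| Creatinine and baseline, no urine output | excluded | kept | creatinine limb can be applied |
| In-hospital creatinine, no 90-day baseline, urine output recorded | unclear: excluded only if baseline counts as creatinine data | kept | kept, fallback screen |
| In-hospital creatinine, no 90-day baseline, no urine output | excluded | unclear, for the same reason | kept, fallback screen |

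The first two rows conflict whatever is decided about baseline. The last two show that the baseline question is open.

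**Step 2. Fallback against the primary endpoint.**

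| | Main definition and primary endpoint | Fallback |
|---|---|---|
| Direction | rise | rise or fall |
| Window | 48 h | hospital stay |
| Reference | baseline from previous 90 days | none stated |
| Decision | stated threshold | review without written criteria |

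**Step 3. The plan's own figure.** Sample Size: 8 covariates × 8 events = 64 events, which reproduces. This point does not change it.

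**Step 4. Scale, for illustration only.** Let *p* be the incidence under the main definition, *m* the share without a baseline, and *c* the confirmed AKI rate among them. Pooled incidence is (1 − m)p + mc, so the shift is m(c − p). I take p = 18.3%, one of the published incidences in the Introduction. The documents give neither *m* nor *c*; both are assumed.

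| m | c = 0% | c = 18.3% | c = 30% | c = 36.6% | c = 54.9% |
|---|---|---|---|---|---|
| 2% | −0.37 | 0 | +0.23 | +0.37 | +0.73 |
| 5% | −0.92 | 0 | +0.59 | +0.92 | +1.83 |
| 10% | −1.83 | 0 | +1.17 | +1.83 | +3.66 |

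(Shift in percentage points.) For example, 0.10 × (0.30 − 0.183) = 0.0117. In a cohort of 64 / 0.183 ≈ 350, itself a back-calculation because the plan sets no total, c = 30% gives a net 0.0023 × 350 ≈ 0.8 to 0.0117 × 350 ≈ 4.1 extra cases.

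For comparison, the 95% half-width at 18.3% and n = 350 is 1.96 × √(0.183 × 0.817 / 350) ≈ 4.1 points.

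The result scales with *p*. With m = 10% and c either 0 or 2p, the shift is about 1.2 points either way at the cited 11.9% and about 3.5 at the cited 35.3%.

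**The case against.** Four stronger readings are tempting, and the documents do not support them.

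- **The two rules flatly contradict each other.** The body exclusion never names the baseline. It can be read as removing only patients with no usable creatinine or urine output, with the renal-function section then handling a missing baseline. That reading is coherent, so the fault on baseline is ambiguity. The *or*/*and* difference is a direct conflict of wording.
- **A creatinine fall is counted as AKI.** The text calls the fallback a screen and requires confirmation, so a fall creates a suspected case. The primary endpoint keeps its 48-hour limit, and entry of fallback cases into the numerator is an inference. What stands is that nothing keeps them out, and the review has no written standard tying it to the 48-hour rise.
- **These patients have no preoperative creatinine at all, so neither the review nor the risk model can use one.** The 90-day limit applies to the baseline. The case report form's preoperative creatinine and eGFR fields carry no time window, so an older value may exist. The postoperative grid also provides for creatinine and diuresis from 6 h, and the urine-output limb needs no baseline.
- **The incidence is biased upwards by a known amount.** The shares and rates are assumed, the direction depends on *c*, and an excess over *p* need not consist of false cases.

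It is also fair that surgery is elective, so few patients may lack a baseline, and that the shifts in most cells of the table are small beside the sampling error.

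**Conclusion.** The point holds as a failure to reconcile eligibility, case definition and endpoint window. The protocol body and the case report form word one exclusion differently, neither says whether a missing 90-day baseline excludes, and the fallback screen does not match the stated 48-hour endpoint. A fall or a late change should not qualify a patient for the primary numerator.

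Its size and direction cannot be fixed from the documents. With p = 18.3% and 2% to 10% without a baseline, the shift is about 1 percentage point or less if 30% of them are confirmed as AKI (0.2 to 1.2). It stays within 1.8 points either way if that rate lies anywhere from 0% to 36.6%. Only a much higher rate, or a higher overall incidence, takes it further. The case for change rests on a reproducible primary endpoint and a cheap remedy more than on a large expected bias.

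**What to change.** 1. Use one exclusion wording in the protocol body and the case report form. It should state whether either or both data types must be missing, and whether a missing 90-day baseline excludes a patient.
2. Limit the primary incidence and the AKI model to patients classifiable by the main definition (rise from baseline, or urine output) within 48 hours. Decide who is classifiable from the data available and never from the result. In particular, say whether a complete urine-output record is enough without a baseline; otherwise such patients could enter only when oliguric, as cases with no matching non-cases.
3. Report the number without a baseline. Give the incidence with and without them in a sensitivity analysis, using a rise within 48 hours only and confirmation criteria written before the records are reviewed.
4. Settle this before the 100-patient pilot, whose event rate depends on it.

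Excluding every patient without a 90-day baseline is one sound choice but not the only one: it would also drop patients whom urine output can classify. The cost is protocol and form wording, plus probably few patients lost from the primary analysis.

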## **SAMPLE SIZE**

Our sample size will be determined to help ensure stability around the point estimates in the final multivariable model. To avoid overfitting our final outcome model, no more than 8 outcome events will be required per covariate of interest. Thus, to fit a model with 8 covariates, we will require approximately 64 outcome events. We will estimate the sample size after a pilot study on 100 patients.

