## **STATISTICAL ANALYSIS**

The statistical analysis will be conducted with the help of Spss software.

Continuous variables are presented through descriptive statistics, including mean, median, variance, minimum and maximum value. Categorical variables are described by the absolute frequencies and percentages.

Data will be examined by T-test or one-way ANOVA (normally distributed variable), Mann-Whitney U test, Kruskal-Wallis one way analysis test (not normally distributed variables), Pearson or Mc Nemar's chi-square test (categorical variables) will be used to evaluate the difference across non-AKI group versus AKI group according to KDIGO criteria or each type of AKI. Two-sided p-values of less than 0,05 were accepted as statistically significant.

Logistic regression analysis will used to build a model of covariates associated with development of AKI and risk of AKI. Likelihood ratio (LR) test statistic, Hosmer-Lemeshow (HL) statistic will used

for assessing goodness of fit (GOF) in the regression models. A discriminatory performance [DP] assessment of the binary logistic model will be performed by classification/diagnostic table, ROC and area under the curve (AUC).

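### The 64-event rule counts covariates in the final model rather than candidate parameters; with the eight unnamed and no selection rule stated, the claimed protection from overfitting is not secured

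*Combined protocol and SAP*

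**What the plan says.** The SAMPLE SIZE section aims at "stability around the point estimates in the final multivariable model". Its rule is: "To avoid overfitting our final outcome model, no more than 8 outcome events will be required per covariate of interest". It concludes: "Thus, to fit a model with 8 covariates, we will require approximately 64 outcome events". No total sample size is given: "We will estimate the sample size after a pilot study on 100 patients".

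The STATISTICAL ANALYSIS section plans univariable tests to "evaluate the difference across non-AKI group versus AKI group according to KDIGO criteria or each type of AKI". The threshold is unadjusted: "Two-sided p-values of less than 0,05 were accepted as statistically significant". A separate paragraph adds: "Logistic regression analysis will used to build a model of covariates associated with development of AKI and risk of AKI". Model checks are the likelihood ratio test, Hosmer-Lemeshow, a classification table and the ROC curve with its AUC. Neither section gives a candidate list, a selection rule, shrinkage, or validation on new or resampled data.

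The SECONDARY ENDPOINTS section makes the identification of AKI risk factors an open aim. The only list of possible covariates is the Case Report Form.

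**The concern.** An events-per-variable rule limits overfitting only if it counts every parameter that the data could have put into the model. If the outcome is used to decide which covariates enter, the search adds optimism that a count of the survivors does not see. The plan ties its 64 events to the final model, leaves the eight covariates open, and describes the model as one made of covariates associated with the outcome.

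At stake is the risk-factor endpoint. Noise variables could be reported as independent risk factors, with a flattering AUC, under a protocol that says overfitting has been avoided.

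**Working it through.** **1. The plan's figure.** 8 events × 8 covariates = 64. This reproduces. The rule is worded as a maximum but used as a minimum.

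**2. Total N implied.** N = 64 / AKI incidence, with incidences from the INTRODUCTION:
- 18.3%: 64/0.183 ≈ 350
- 35.3%: 64/0.353 ≈ 182
- 11.9%: 64/0.119 ≈ 538

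**3. Possible candidates in the CRF.** Preoperative items: 4 demographic + 20 comorbidities + 4 (ASA, Karnofsky, ECOG, weight loss) + 10 medications + 8 laboratory + 3 cardiovascular + 3 respiratory = 52. Intraoperative items: 29 (one per question), 33 (some doses counted separately) or 44 (every box). The totals are 81, 85 and 96. This is an upper bound on the pool, because items overlap (creatinine and eGFR, Karnofsky and ECOG, drug use and dose) and some are constant or nearly so (dialysis, given the exclusion criteria; active solid neoplasm in a cancer cohort).

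**4. Analytic check.** With k independent null candidates tested at 0.05, the expected number of false associations is 0.05k and the chance of at least one is 1 − 0.95^k. For k = 84 these are 4.2 and 98.7%. For k = 8 they are 0.4 and 33.7%.

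**5. Null simulation.** There is no true risk factor, 64 events and N = 350. Candidates are screened at p<0.05, at most eight are kept, and the logistic model is refitted. A false factor is a term with p<0.05 in the refit. The ranges span separate runs, with candidates either independent or moderately correlated (latent correlation 0.5 in groups of four, an assumption). The lower ends depend on that correlation.

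| Candidates | 64 / candidates | False factors per study | Studies with at least one |
|---|---|---|---|
| 84 | 0.76 | 2.4–3.2 | 92–98% |
| 40 | 1.6 | 1.4–1.7 | 82–85% |
| 20 | 3.2 | 0.7–0.9 | 53% (correlated) |
| 12 | 5.3 | 0.4–0.6 | 37% (correlated) |
| 8 prespecified, all entered | 8.0 | about 0.36 | about 30% |

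**6. With some true predictors.** This run assumes four true predictors, each shifted by 0.35 SD, independent normal candidates, N = 350, and the eight strongest univariable associations entered. The prespecified eight include the four true ones, which favours prespecification.

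| Model | Apparent AUC | AUC in new data | Calibration slope |
|---|---|---|---|
| 8 prespecified | 0.715 | 0.668 | 0.77 |
| Best 8 of 84 | 0.765 | 0.618 | 0.41 |

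The slope for the best eight is 0.49 from 40 candidates, 0.60 from 20 and 0.69 from 12. With 84 candidates, N = 182 and N = 538 give slopes of 0.31 and 0.43.

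**The case against.** The strongest reply is that the plan never says it will screen. The group comparisons and the regression stand in separate paragraphs, with no threshold, stepwise procedure or candidate pool linking them. The phrase about covariates of interest could mean eight chosen in advance, and then 64 events satisfy the plan's rule. This stands as a limit on the point: selection from the CRF is a reading, not a stated method. It does not clear the plan, because no list of eight exists to secure the favourable reading.

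Four stronger readings are tempting and are not supported:
- A reader might infer that the plan prescribes picking from about 84 items. The CRF is a data-collection form, not a candidate list.
- A reader might take 64/84 ≈ 0.8 as the actual number of events per candidate. It is a worst case, since the effective pool is smaller. At about 12 candidates the excess of false factors is small.
- A reader might put a figure on the parameters that eight covariates would cost, because anesthesia type and surgery type have several categories. Covariates and parameters do differ, but none of the eight is named, so no figure follows.
- A reader might infer odds ratios inflated by a known amount. None was measured here.

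Prespecification is not free of error either: about 30% of null studies with eight named covariates still show at least one false factor. A global null is also the extreme case. Apparent AUC alone can miss the problem: 40 screened candidates gave about 0.61 under the null, much the same as eight prespecified.

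**Conclusion.** The concern holds in this form: the 64 is arithmetically right but counts the wrong thing, and the plan does not secure the protection from overfitting that it claims. If covariates are selected from the CRF by their association with AKI, false independent factors under the null rise from about 0.36 per study with eight prespecified to 0.7–0.9 with 20 candidates and 2.4–3.2 with 84. If eight parameters were fixed in advance, the rule would be met.

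The size rests on assumptions that the documents do not settle: the pool, the correlation between candidates, selection at p<0.05, and N = 350 from the 18.3% incidence. The direction is the same at every pool size examined, though little remains at 12. The risk-factor secondary endpoint is affected. The primary endpoint, AKI incidence within 48 hours, is not. The change should be made, with medium confidence, because it resolves either reading of the text.

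**What to change.** **SAMPLE SIZE.** Replace the wording that sets eight as a maximum. Require at least eight outcome events per candidate parameter, with each dummy variable or non-linear term counted as one.

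**STATISTICAL ANALYSIS.**
- Name at most eight candidate parameters, chosen on clinical grounds, before any AKI versus non-AKI comparison is run, including in the 100-patient pilot.
- Enter all of them, with no screening by p-value.
- Report the other CRF variables descriptively.
- If a larger pool is wanted, list it, fit ridge or LASSO logistic regression, label the result exploratory, and report bootstrap optimism-corrected AUC and calibration, with the whole procedure repeated in each resample.

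**Cost.** A few sentences of wording and one investigator meeting to choose the candidates; no extra patients are needed. The downside is that variables outside the named set can be reported only as exploratory.

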## **PRIMARY ENDPOINTS**

- To evaluate the incidence of postoperative AKI according to KDIGO criteria within 48 hours after surgery

## **SECONDARY ENDPOINTS**

- Distinction between transient and persistent AKI
- Occurrence of recovery or progression at 7 days, 30 days and 3 months
- Association between AKI and pulmonary complications, major adverse cardiovascular events, anastomotic or septic complications, or death.
- Identify risk factors associated with AKI occurrence.

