### **Assessment of complications and mortality**

Postoperative pulmonary complications were identified and categorized based on European Perioperative Clinical Outcome (EPCO) definitions from the ESA-ESICM joint taskforce on perioperative outcome measures. These include respiratory infection, respiratory failure, pleural effusion, atelectasis, pneumothorax, bronchospasm, aspiration pneumonitis.

Major adverse cardiac and cerebrovascular events (MACCE) was a composite outcome of non-fatal cardiac arrest, acute myocardial infarction, congestive heart failure, new cardiac arrhythmia, angina, ischemic stroke.

Sepsis was defined according Sepsis-3 definition.

We performed separate analyses of complications apparently related to surgical technique (for instance, anastomotic leakage, fistula, abscess, hemorrhage) and medical complications, i.e. pulmonary, cardiovascular (acute myocardial infarction, atrial fibrillation, cardiogenic shock) and septic.

All complications were evaluated 30 days after surgery.

Mortality in hospital after resection of esophageal cancer was defined as any death during the admission when the operation was performed. This was more reliably quantified than 30-day mortality.

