### COMORBIDITIES:

- COPD Gold class \_\_\_\_
- Interstitial Lung Disease
- pulmonary hypertension
- asthma
- active smokers
- dyspnea
- stroke/TIA
- coronary artery disease
- DM
- hypertension with medication
- active solid organ neoplasm
- hematologic neoplasm
- disseminated cancer
- alcohol use disorder
- dementia
- congestive heart failure in 30 days prior to surgery
- dialysis
- ascites within 30 days prior to surgery
- systemic sepsis within 48 hours prior to surgery
- ventilator dependent

ASA class \_\_\_\_\_

Functional status: Karnofsky \_\_\_\_\_ ECOG \_\_\_\_\_

Weight loss within the last 3 months \_\_\_\_\_

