**POSTOP :**

	6h	12h	24h	48h	72h	4d	5d	6d	7d	ICU discharge	H discharge	30d	1y
sCr													
eGFR													
urea													
Troponin													
BNP													
Hb													
NGAL													
diuresis													
Fluids in													
drainages													
diuretics													
vasopressors													
inotropes													

\*NA if not present in the medical records

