**Outcomes:**

need for RRT: \_\_\_\_\_days

MACCE within 30 days:  AMI

congestive heart failure

non-fatal cardiac arrest

new cardiac arrhythmia

angina

stroke

pulmonary complications within 30 days:  respiratory infection at \_\_\_\_day (i.e. patients has received antibiotics for a suspected respiratory infection + one of the following: new or changed sputum, new or changed opacities, fever, wbc >12000)

respiratory failure at \_\_\_\_day (PaO2 < 60 mmHg at room air, a P/F < 300 mmHg or SpO2 <90% requiring oxygen therapy)

pleural effusion at \_\_\_\_day

atelectasis at \_\_\_\_day

pneumothorax at \_\_\_\_day

bronchospasm at \_\_\_\_day (bronchodilators treatment for new expiratory wheezing)

aspiration pneumonitis at \_\_\_\_day

length of CMV \_\_\_\_h

need for NIV in \_\_\_\_\_h

surgical complications within 30 days:  fistula       hemorrhage       abscess

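### The case report form has no field for two stated secondary endpoints (3-month renal recovery, postoperative sepsis) and leaves the urine-output input to the primary endpoint undefined

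*Combined protocol and SAP*

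**What the plan says.** Data Collection states that a trained team enters each patient's data in the CRF, with an electronic copy kept in Excel. The CRF is therefore the source of the analysis file.

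- **Renal course.** Secondary Endpoints lists "Occurrence of recovery or progression at 7 days, 30 days and 3 months". The last four columns of the CRF's Postop grid are "ICU discharge H discharge 30d 1y".
- **Sepsis.** Secondary Endpoints asks for the association of AKI with "anastomotic or septic complications, or death", among other outcomes. Assessment of complications and mortality adds "Sepsis was defined according Sepsis-3 definition" and "All complications were evaluated 30 days after surgery", and makes septic events one of the medical complication categories. The CRF Outcomes page has blocks headed "MACCE within 30 days" and "pulmonary complications within 30 days", and a third for surgical complications. The only item on the form that names sepsis is under Comorbidities: "systemic sepsis within 48 hours prior to surgery".
- **Urine output.** The primary endpoint is AKI by KDIGO within 48 hours of surgery. Assessment of renal function lets AKI be met by a creatinine rise or by urine output below 0.5 mL/kg/h for 6 h. The Postop grid has a row labelled diuresis with no unit and no interval. The intraoperative diuresis item, by contrast, is a total in ml.
- **Missing data.** The protocol's exclusion criterion joins creatinine and urine output with *or*. The CRF's version joins them with *and*.

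**The concern.** An endpoint with no field on the form reaches the analysis only through steps that the plan does not describe. For 3-month recovery and for sepsis, the analyst would have no recorded value and would need either a second chart review or a derivation rule written after the data are in hand.

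The urine-output question is of a different kind, because the row exists. What a cell contains is not stated, and the columns become wider apart after 12 h. If the cells are totals, a patient who meets the 6-hour criterion without a creatinine rise can look normal on the form. That would affect the primary incidence, and also the AKI grouping on which every association analysis rests.

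**Working it through.** **1. Recovery time points against the grid.** The columns are 6h, 12h, 24h, 48h, 72h, 4d, 5d, 6d, 7d, ICU discharge, hospital discharge, 30d and 1y, which is 13. Of the three endpoint times, 7 days and 30 days each have a column and 3 months has none. The 1-year column serves no stated endpoint. The footnote on values absent from the records covers an empty cell, not an absent column.

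**2. Complication groups against the Outcomes page.**

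| Group required | Block within 30 days |
|---|---|
| Cardiovascular (MACCE) | yes |
| Pulmonary | yes |
| Surgical, including anastomotic | yes |
| Septic | none |

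Respiratory infection, abscess, vasopressor use, creatinine and the organ-dysfunction complication grades are recorded. Nothing in the document links any of them to a sepsis diagnosis or its onset.

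**3. Urine output in 0-48 h.** The columns at 6, 12, 24 and 48 h bound intervals of 6, 6, 12 and 24 h. There are 48 / 6 = 8 consecutive 6-hour blocks. How many the form shows depends on what a cell means:

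| Assumed cell content | 6-h blocks seen, of 8 |
|---|---|
| Rate at that moment | 0 |
| Interval or cumulative total | 2 (0-6, 6-12 h) |
| Preceding 6 h | 4 (0-6, 6-12, 18-24, 42-48 h) |
| Lowest 6-h rate since the previous column | 8 |

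Even the last reading can miss a spell that straddles a column time, unless each 6-hour window is assigned to the column in which it ends.

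*Masking on the totals reading.* Let a 6-hour spell run at rate r inside an interval of L hours. The interval mean is not below 0.5 when the remaining hours average at least (0.5 × L − 6r) / (L − 6). The values of r are assumptions.

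| r (mL/kg/h) | 12-24 h cell: (6 − 6r) / 6 | 24-48 h cell: (12 − 6r) / 18 |
|---|---|---|
| 0 | 1.00 | 0.67 |
| 0.25 | 0.75 | 0.58 |
| 0.4 | 0.60 | 0.53 |

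The calculation is per kilogram. Body weight is on the CRF, so weight is not the gap.

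*Limit in the other direction.* If a 12-h or 24-h mean is below 0.5, at least one of its 6-hour blocks must be below 0.5. On the totals reading, the form can therefore confirm the criterion after 12 h in some patients but cannot rule it out.

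**4. Would fixed 6-hourly columns be enough?** No. Assume zero output from 9 to 15 h and 1.0 mL/kg/h otherwise. Blocks 6-12 h and 12-18 h each hold 3 h at 1.0 and 3 h at 0, so each averages 3 / 6 = 0.5. Neither is below 0.5, although a full 6 hours had no output.

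**5. Missing-data rule.** Take a patient with creatinine but no derivable 6-hour urine output. Read literally, the protocol's *or* excludes the patient, which changes the denominator. The CRF's *and* keeps the patient, classified on creatinine alone, which may change the numerator.

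**The case against.** The strongest reply is that the study is retrospective. Charts can be re-read, the team is trained, and Assessment of renal function describes case-by-case review of suspected AKI. This holds in part. Re-reading is possible, which is a reason to correct the form before charts are opened. The team's instructions are not in the document, and nothing there describes extracting data for a column or block that the form does not print. The case review may cover only patients without a baseline creatinine, and it cannot recover an oliguric spell that no one suspected.

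The second reply is that part 3 is not a mismatch, and this stands. The diuresis row is on the form with four cells in the primary window. The defect is an undefined cell. The creatinine arm is well served, with a preoperative value and cells at 6, 12, 24 and 48 h.

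A reader might also infer that the sepsis components on the form are insufficient for Sepsis-3. The documents name that definition but do not list its components, so they do not settle this. What they show is that no postoperative sepsis diagnosis or onset is recorded.

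**Conclusion.** Two omissions are read directly from the form: 1 of 3 recovery time points has no column, and 1 of 4 complication groups has no outcome block. Both affect secondary endpoints, and confidence in them is high. The grid's header is continuous from 30 days to 1 year, so a column lost in PDF conversion is unlikely, though it cannot be excluded.

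The third element is an ambiguity that bears on the primary endpoint. Its harm depends on the cell holding totals, the preceding 6 h or a momentary rate.

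A reader might go further and conclude that the form cannot capture urine-output AKI, or that incidence will be underestimated. The documents support neither. A suitable cell definition would recover most or all 6-hour periods. The net direction of bias is open because it also depends on which missing-data rule is applied. The block counts and masking thresholds describe what the form can show, not how many patients would be misclassified, and that number cannot be sized from the documents.

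This should be fixed. No design figure in the plan changes.

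**What to change.** Before abstraction, or at the latest at the 100-patient pilot announced under Sample Size:

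1. Add a 3-month column for creatinine and eGFR. The 1-year column may stay.
2. Add an outcome item: postoperative sepsis (Sepsis-3) within 30 days, yes/no, with day of onset.
3. State the unit and interval of the diuresis cell, and add the lowest urine output over any 6-hour period in 0-48 h (mL/kg/h), with its start time. Fixed 6-hourly columns are not a substitute.
4. In AKI cases, record urine output beyond 48 h on the same basis, so that transient and persistent AKI can be separated by the urine criterion in Assessment of renal function.
5. Use one wording of the missing-data exclusion in the protocol and the CRF, and say how a patient with creatinine but no derivable 6-hour urine output is handled.

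If the records do not hold these data, or abstraction is already complete (the complications section is written in the past tense), restate the affected endpoints to what was extracted and report AKI by creatinine and by urine output separately.

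The cost is a form revision and extra chart reading per patient, mainly for urine output. No new patients or procedures are needed. If charts have already been read, reopening them costs more, and restating the endpoints is the cheaper course.
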